7.4. Tolerability and Treatment Compliance

7.4.1. Tolerability

Tolerability will be assessed based on percentage of subjects that complete the 12-month treatment period of the study and the percentage of subjects who discontinue from the 12-month treatment period due to a TEAE. Time (days) from enrolment to discontinuation will be illustrated as Kaplan-Meier curves by treatment regimen. Patients who complete the study will be right censored at the date of last dose of study treatment during the 12-month study period. Time to discontinuation will also be explored by recruitment wave 1 and 2 following corrective actions for patients' retention.

7.4.2. Treatment Compliance

The proportion of used medication out of scheduled medication will be calculated based on the actual daily administered LD dose of ND0612 and summarized with descriptive statistics. The scheduled daily medication dose will be 720 mg LD for Regimen 1 and Regimen 3 and 537.6 mg LD for Regimen 2. The total scheduled dose will be calculated as duration of treatment (as calculated in section 7.2) multiplied by the scheduled daily dose.

In addition, the number and proportion of patients with at least one prolonged treatment interruption (over 3 hours, as recorded on the corresponding CRF page) and the total number of prolonged treatment interruptions will be tabulated.

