8 INVESTIGATIONAL PLAN

8.1 Overall Study Design and Plan: Description

8.1.1 Study Design

A multi-center, international, open-label, safety study of ND0612, a solution of LD/CD delivered via a pump system as a continuous SC infusion in subjects with advanced PD. The study will assess safety, tolerability, and efficacy of 2 dosing regimens (Regimen 1 and 2) of ND0612 compared to standard oral LD/DDI (Baseline) in advanced PD subjects. Two cohorts of subjects are candidates for this study:

Cohort 1 includes subjects with advanced PD who completed the treatment period in study ND0612H-006 within one month prior to enrollment in ND0612H-012. The subjects who completed treatment in study ND0612H-006 and who are considered capable of handling the procedures related to the administration of the SC infusion alone or with the assistance of a study partner can either roll-over directly to the current study or roll-over within a month time window. In the current study, subjects were to receive the same treatment regimen that they received in the ND0612H-006 study (including any up- or down-titrations performed in study ND0612H-006). On 08 December 2016, the Sponsor decided to switch all subjects who were treated with Regimen 2 to Regimen 1. Following this decision, ongoing subjects treated with Regimen 2 were to be switched at their next scheduled study visit to Regimen 1. Subjects may proceed directly to the Baseline visit of the current study (which may be the same as the end of treatment period visit for the ND0612H-006 protocol); a Screening Visit is not necessary.

Subjects in Cohort 1 who do not enroll to ND0612H-012 immediately upon completion of the treatment period in ND0612H-006 will perform the Baseline visit of ND0612H-012 in the morning, after having taken their standard anti-PD medication. During the visit, treatment with the pump system will be started. It is anticipated that subjects will down titrate their oral LD/DDI based on the investigator's clinical judgment. Subjects may be asked to perform additional unscheduled visits in cases the investigator believes the subject's treatment requires additional titration to achieve stabilization.

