- 4. Titrate the dose of adjunct oral LD/DDI, and the ND0612 dose based on the subject's individual clinical response and tolerability until a stable daily regimen is maintained.
- 5. Extra doses of oral LD/DDI can be used to manage "OFF" symptoms that are not controlled by the continuous ND0612 infusion

ND0612 dose may be decreased if required per the Investigator's decision. In the event a subject experiences dopaminergic complications, oral LD/DDI taken as additional therapy (if any) should be reduced/stopped first. If complications persist, the hourly high infusion rate may be down titrated. Every 0.05 ml/h increment is equivalent to \sim 50 mg LD reduction per day. There is no cap to the number of dose reductions a subject may require. Subjects tolerating a dose reduction for 72 hours may attempt to up-titrate again. Subjects must come to the clinic for any up or down titrations as the pump must be reprogrammed to accommodate the new flow rate.

Abrupt discontinuation or significant dose reductions of the study treatment should be avoided. The study drug dosing should be gradually reduced.

In case of any problem in the pump system that cannot be fixed within 3 hours, the subjects should contact the Investigator and the helpline, and resume a regimen of oral LD/DDI until the study drug administration can be continued.

Study drug and clinical supplies for 1 month will be dispensed on the clinic visits at Baseline and Months 1, 2, 3, 4, 6, 9. On months 5, 7, 8, 10, 11, study drug and clinical supplies for 1 month will be dispensed to the subject, or the study partner at a clinic visit dedicated to study medication dispensing, Alternative means of medication distribution (e.g., via courier) may be used following regulatory and EC approval.

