8.4.9.3 Down Titration of Study Drug During the Treatment Period of the Study

ND0612 dose may be decreased if required per the Investigator's decision. In the event a subject experiences dopaminergic complications in the opinion of the clinical investigator, oral LD/DDI or entacapone taken as additional therapy (if any) should be reduced/stopped first. If complications persist, the hourly high infusion rate may be down titrated. Every 0.05 mL/hr increment of ND0612 infusion rate is equivalent to ~50 mg LD reduction per day. There is no limitation to the number of dose reductions a subject may require. Subjects not tolerating a dose reduction may attempt to up-titrate again. Both down and up titrations of study drug and additional therapy are at the discretion of the investigator. The morning dose of oral LD/CD IR in Regimen 3 is not to be reduced. Subjects must come to the clinic for any up or down titrations of the study drug as the pump must be reprogrammed to accommodate the new flow rate.

Subjects with a low total dose of LD at baseline (\leq 700 mg per day) should receive special consideration. In such cases, upon initiation of SC infusion on Day 1, oral LD/DDI may be significantly reduced or stopped (please note the morning dose of Regimen 3 must be taken); the ND0612 hourly high infusion rate may be down titrated as well.

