8.4.10 Study Drug Accountability and Treatment Compliance

Drug accountability measures will be performed as described in Section 13.1.

During the study visit the investigator and/or site coordinator will assess the subject's compliance with the prescribed regimen for the study medication. This will include checks of protocol compliance and use of study drug in order to assess the reliability of subject-generated data. Subjects who fail to comply with the study requirements may be withdrawn from the study, following consultation with the sponsor.

Compliance with the dosing regimen will be determined by performing study drugs accountability of returned study drugs used and unused. The number of used, unused and lost vials and/or containers will be recorded on the accountability forms by site personnel.

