3.2.3.13. Change in SGI-Improvement from Baseline to the 12 month visit.

- This variable will be derived in a similar way as CGI-I described in 3.2.3.12.

3.2.3.14. Change in PDSS total score from Baseline to the 12 month visit.

- Each of the 15 items is scored on a 5-point scale (from 0 indicating no symptoms to 4 indicating maximum symptoms). The total score is calculated as a sum score of the 15 items. In case a single item is missing, the total score will be set as missing.

3.2.3.15. Change in UPDRS Part III (motor score) from Baseline to the 12 month visit.

- The UPDRS part III (motor) score will be calculated as the sum of the individual items 18-31. UPDRS scores will be gathered during visit but not at pre-specified time points. Missing individual items will not be imputed. If there is at least 1 missing item, the corresponding sum score will be set as missing.

3.2.3.16. Change in ND0612 Dose - Data on ND0612 dose reduction will be assessed as change from baseline in total daily of LD dose.

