7.2. Study Drug Administration

Duration of treatment (days treated) is the number of days on treatment based on the first and last days of treatment with the study drug (last day of study drug – first day of study drug + 1).

The following information will be summarized by treatment regimen and overall.

- The number of patients exposed to study treatment
- Mean Duration of exposure (days)

- Total exposure to study treatment, expressed as person years (sum of exposure to study treatment over all patients, classified by treatment regimen)
- Number of patients who reduced ND0612 dose and the mean reduction from baseline to each visit

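### SAP 7.4.2 labels administered levodopa over a fixed 720 mg a day as treatment compliance, so a prescribed rate reduction is counted like a missed infusion

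*SAP*

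**What the plan says.** SAP 7.4.2 compares the ND0612 LD actually administered with the LD scheduled. For the denominator, "The scheduled daily medication dose will be 720 mg LD for Regimen 1 and Regimen 3"; Regimen 2 has 537.6 mg. Then: "The total scheduled dose will be calculated as duration of treatment (as calculated in section 7.2) multiplied by the scheduled daily dose". Under SAP 7.2, duration is the last treatment day minus the first, plus one. No term covers a change in the prescribed rate. The same section also tabulates interruptions longer than 3 hours.

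The protocol treats the rate as adjustable:

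- Section 8.4.1: "There is no cap to the number of dose reductions a subject may require".
- Section 8.4.9.3, on Day 1 for subjects taking 700 mg LD a day or less at baseline: "the ND0612 hourly high infusion rate may be down titrated as well".
- Section 8.1.1: Cohort 1 continues the regimen of the earlier study, "including any up- or down-titrations performed in study ND0612H-006".
- The synopsis gives the Regimen 1 day rate and the Regimen 3 daily volume as maxima.

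Protocol 8.4.10 has site staff assess "compliance with the prescribed regimen for the study medication" at visits and determines compliance from drug accountability.

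Dose reduction is reported elsewhere. SAP 7.2 lists "Number of patients who reduced ND0612 dose and the mean reduction from baseline to each visit", and SAP 3.2.3.16 adds: "Data on ND0612 dose reduction will be assessed as change from baseline in total daily of LD dose".

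**The concern.** A compliance figure should tell the reader how much of what was prescribed was taken. Here the denominator is the full-rate dose, whatever the investigator programmed. A subject moved to a lower rate who then misses nothing scores below 100%, and the score cannot be told apart from that of a full-rate subject who skipped infusion days.

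This matters most where the rate was lowered for tolerability. In a safety and tolerability study, a reduction made because of dyskinesia or another levodopa effect says something about the drug. Under this heading it would look like poor adherence by the subject.

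**Working it through.** **Inputs.** LD concentration is 60 mg/mL (Protocol 8.4.2). Rates and hours come from Protocol 8.1.1 and Table 2. The titration step is 0.05 mL/h, put at about 50 mg LD a day (Protocol 8.4.9.3). The number of steps, their timing and 365 days on treatment are my assumptions.

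**Step 1: reproduce the plan's scheduled doses** (sum of rate × hours × 60).

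- Regimen 1: (0.08 × 6 + 0.64 × 18) × 60 = 12.00 × 60 = 720 mg
- Regimen 2: 0.64 × 14 × 60 = 537.6 mg
- Regimen 3: 0.75 × 16 × 60 = 720 mg

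All three agree with SAP 7.4.2.

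**Step 2: prescribed dose after n steps.**

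- Regimen 1 (day rate only): 60 × [0.08 × 6 + (0.64 − 0.05n) × 18] = 720 − 54n mg
- Regimen 3: 60 × 16 × (0.75 − 0.05n) = 720 − 48n mg

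Steps of 54 and 48 mg fit the protocol's approximate 50 mg.

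**Step 3: SAP ratio for a subject who infuses everything prescribed.** With d full-rate days before the reduction and L the reduced daily dose, ratio = [720d + L(365 − d)] / (720 × 365).

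| Regimen, steps | L (mg) | d = 0 | d = 30 | d = 90 | d = 180 |
|---|---|---|---|---|---|
| 1, one step | 666 | 92.5% | 93.1% | 94.3% | 96.2% |
| 1, two steps | 612 | 85.0% | 86.2% | 88.7% | 92.4% |
| 1, three steps | 558 | 77.5% | 79.3% | 83.0% | 88.6% |
| 3, one step | 672 | 93.3% | 93.9% | 95.0% | 96.6% |
| 3, two steps | 624 | 86.7% | 87.8% | 90.0% | 93.2% |
| 3, three steps | 576 | 80.0% | 81.6% | 84.9% | 89.9% |

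Against the dose prescribed each day, every cell would be 100%.

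**Step 4: the equivalent in missed days.** One step from Day 1 gives the same score as a full-rate subject missing (1 − 666/720) × 365 = 27.4 days in Regimen 1, or (1 − 672/720) × 365 = 24.3 days in Regimen 3.

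**Step 5: two related cases.**

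- *Switched subjects.* Twelve subjects were in Regimen 2 when it was stopped and two had already discontinued (Protocol 8.4.5), so 12 − 2 = 10 moved to Regimen 1. SAP 7.4.2 gives both daily doses but no rule for splitting their duration.
- *Bedtime removal.* Regimen 3 subjects may take the pump off at bedtime before 16 hours have passed. With 15 or 14 hours at full rate (assumed), the score is 675/720 = 93.8% or 630/720 = 87.5%. A denominator built on programmed hours gives the same result, so the fix does not cure this.

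**The case against.** The strongest reply is that the SAP does what it says. The text of SAP 7.4.2 describes the quantity as used over scheduled medication and states the scheduled doses. Those doses are the totals in Protocol Table 2. In these documents a dosing regimen usually means Regimen 1, 2 or 3, and Protocol section 11 defines no compliance analysis.

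That stands against one tempting inference, that the SAP plainly contradicts the protocol. It does not: whether the prescribed regimen in 8.4.10 means the nominal or the titrated dose is arguable. Section 8.1.1 supports the titrated reading, because it counts earlier titrations as part of the regimen Cohort 1 receives. The concern does not need that contradiction. A ratio headed compliance that falls when a subject follows the investigator's instruction is misleading on either reading.

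A second reply is that the components are visible: dose reductions (SAP 7.2, 3.2.3.6, 3.2.3.16), adverse events leading to dose adjustment or temporary withdrawal (7.3.4), and interruptions over 3 hours (7.4.2). They give context, but none enters the ratio, so the reader cannot recover adherence from it.

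A third reply is that the Day 1 figures are at the upper end. Oral LD is to be reduced first, a lower rate on Day 1 is optional, and the rate may be raised again. This is fair, and the later-onset columns show the smaller effect.

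A fourth reply concerns the remedy. The documents do not say how daily administered dose is captured. Accountability counts vials, and the Pump Diary records only stops of more than 3 hours. If the recorded dose is simply the programmed dose, a prescribed-dose denominator would put everyone near 100% and carry no information. This stands, and the fix has to allow for it.

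**Conclusion.** The point holds as a minor one. For Regimens 1 and 3 the ratio in SAP 7.4.2 measures dose received relative to full dose, and its heading presents it as adherence. The direction is certain if the numerator is the LD actually infused or programmed: any prescribed reduction lowers the score. The size depends on assumed steps and timing. One step in force throughout gives 92.5% or 93.3%; one step after 180 full-rate days gives 96.2% or 96.6%.

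A reader might infer that overall compliance will be badly understated. The documents give no frequency of down-titration, so the effect on the summary statistic cannot be sized. A reader might also infer that subjects will be misclassified or the safety results distorted. Neither follows. SAP 7.4.2 sets no cut-off, no analysis set in SAP section 4 depends on compliance, and adverse event rates use exposure time rather than dose. Only one descriptive summary changes.

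**What to change.** **Where administered dose is captured independently of the programmed dose** (for example from vial accountability or recorded interruptions), replace the definition in SAP 7.4.2 with: *The total scheduled dose is the sum, over treatment days, of the LD dose prescribed for that day, i.e. the sum over programmed rates of rate × hours × 60 mg/mL, updated at each titration visit.* This covers the night and day rates of Regimen 1 and the change from 537.6 to 720 mg in the ten switched subjects. Report administered LD / (720 mg × duration) on its own line as *relative dose*.

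**Where programmed dose is not recorded, or the recorded administered dose is only the programmed dose**, keep the present ratio, report it as *relative dose*, and describe adherence from the interruptions over 3 hours and vial accountability.

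**Footnote**, if the prescribed-dose ratio is used: *Permitted pump removal at bedtime in Regimen 3, and in Regimen 2 while it was given, can still lower this ratio.*

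**Cost.** SAP text and one table program before database lock, with no protocol change. SAP 7.2 and 3.2.3.16 already need dose by visit, but the documents describe no field for daily programmed dose, so check the eCRF first. The fallback changes a label and relies on data already collected. If the database is already locked, Protocol 11.1 provides for recording departures from the SAP in the study report, and the relabelling can be made there.

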7.5. Secondary Safety Analyses

C-SSRS: The C-SSRS is a measure of suicidal ideation and behavior. The rating scale has 4 general categories: suicidal ideation, intensity of ideation, suicidal behavior, and actual attempts. All C-SSRS data will be listed. The frequency and percentage of patients with each response for suicidal ideation, intensity of ideation, and suicidal behavior items will be summarized as appropriate by visit.

QUIP: The QUIP is an instrument used to measure the extent of impulsive and compulsive behaviors in PD patients. The QUIP has 3 sections: Section 1 assesses any impulsive control disorder (gambling, sexual, buying, and eating disorders); Section 2 assesses other compulsive behaviors (punding, hobbyism, and walkabout); and Section 3 assesses compulsive medication use. All QUIP scores (A: gambling, B: sex, C: buying, D: eating, total ICD score (A-D), E: hobbyism-punding, F: PD medication use and total QUIP score (A-F)) will be summarized with descriptive statistics by visit. In addition, the changes from baseline will be summarized.

ESS: The ESS is used to determine the level of daytime sleepiness. There are 8 situations listed for which patients rate their likelihood of dozing or sleeping (0=would never doze or sleep, 1=slight chance of dozing or sleeping, 2=moderate chance of dozing or sleeping, and 3=high chance of dozing or sleeping). The total score is the sum of 8 item scores and can range between 0 and 24. If any item score is missing, the total score will be missing. The higher total score indicates the higher level of daytime sleepiness. A score of 10 or more is considered sleepy, and a score of 18 or more is very sleepy. The ESS score will be summarized with descriptive statistics by visit. In addition,

the proportion of patients who are sleepy (score of 10 or more) or very sleepy (score of 18 or more) will be tabulated by visit and treatment group.

The influence of the pump system malfunctions on the safety of ND0612 will be evaluated by capturing data on the date and time of malfunctions, including the description of the malfunction, association to an AE and the action taken. All data collected for the pump system malfunctions will be listed. In addition, the following will be tabulated by treatment group:

- The number of pump system malfunctions and the number of subjects with at least one pump system malfunction
- The number of pump system malfunctions associated with an AE and the number of subjects with at least one pump system malfunction associated with an AE
- The distribution of the actions taken regarding the malfunctions (both as subject and event counts).

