10.1.10 Assessment of Impulsive-Compulsive Disorders in PD-Rating Scale (QUIP-RS)

The QUIP-RS, see Appendix 17.4) is designed to measure severity of symptoms and support a diagnosis of impulse control disorders and related disorders in PD. It assesses gambling, sexual, buying, and eating behaviors, other compulsive behaviors and compulsive medication use on a scale from 0 ("never") to 4 ("very often"). The QUIP-RS will be applied on scheduled clinic visits on Day 1, Week 1, Months 1, 2, 3, 4, 6, 9, 12, Safety FU 1, and Early Termination visit (if applicable).

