11.1.3.2 Secondary Safety Measures

The secondary safety endpoints to be assessed for the 12-month treatment period include:

- Assessment of suicidal behavior and ideation (C-SSRS responses, including the number of subjects experiencing at least 1 event of suicidal ideation, at least 1 event of suicidal behavior, at least 1 event of suicidal ideation or behavior and self-injurious behavior without suicidal intent, changes from Baseline in C-SSRS categories (No Suicidal Ideation or Behavior, Suicidal Ideation and Suicidal Behavior) and changes from Baseline in C-SSRS suicidal ideation)
- Assessment of impulsive compulsive behavior (QUIP-RS total scores)
- Epworth Sleepiness Scale (ESS total score)
- Vital signs with a focus on orthostatic BP (possible dopaminergic side effect)
- Laboratory data (hematology and biochemistry), including dipstick urinalysis results evaluation
- 12-lead ECG parameters, including ECG interpretation of clinical significance
- Physical examination
- Prior and concomitant medications

The definition of the other safety endpoints and the corresponding analyses will be detailed in the SAP.

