11.1.4.2 Secondary Safety Analysis

The definition of the other safety endpoints and the corresponding analyses will be detailed in the SAP.

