5. GENERAL ASPECTS FOR DATA ANALYSIS

5.1. General Methods

All data from all patients entered into the study will be included in patient data listings. The listings will be sorted by center, and patient number (and by visit, if applicable).

The data will be summarized using either descriptive statistics (number of non-missing observations, mean, median, SD, standard error of the mean (SEM), minimum and maximum) for continuous data or frequency counts and percentages for categorical data. For visit-specific data, the number of subjects with non-missing observations at the visit in question will be used as the denominator for percent calculations. Unknown, Not Done, Not Applicable and other classifications of missing data will not be considered.

The summaries will be broken down by treatment regimen (Regimen 1, Regimen 3) and by visit, as applicable. For demographic and other baseline characteristics and selected safety data, an overall column will be displayed in addition to the data broken down by the treatment regimen. Unscheduled or repeated assessments will not be included in summary tables but will be included in listings.

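### QUIP-RS is summarised only as a continuous score, so no planned table counts the subjects who develop new or worsened impulsive-compulsive symptoms

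*SAP*

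**What the plan says.** Protocol 7.2 and SAP 2.2 name QUIP-RS among the further (secondary) safety objectives at 12 months. Protocol 10.1.10 says that the scale "is designed to measure severity of symptoms and support a diagnosis of impulse control disorders and related disorders in PD", and schedules it on Day 1, at Week 1 and Months 1, 2, 3, 4, 6, 9 and 12, at the first safety follow-up visit and at early termination.

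The protocol's endpoint is "Assessment of impulsive compulsive behavior (QUIP-RS total scores" (section 11.1.3.2). For the method it defers: "The definition of the other safety endpoints and the corresponding analyses will be detailed in the SAP" (section 11.1.4.2).

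SAP 7.5 covers domains A to F, the ICD total (A-D) and the overall total. The plan for these is "total QUIP score (A-F)) will be summarized with descriptive statistics by visit. In addition, the changes from baseline will be summarized". SAP 5.1 defines descriptive statistics for continuous data as "number of non-missing observations, mean, median, SD, standard error of the mean (SEM), minimum and maximum". It also states: "All data from all patients entered into the study will be included in patient data listings", and "Unscheduled or repeated assessments will not be included in summary tables but will be included in listings".

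Neither document sets a threshold, a shift table or a definition of new or worsened symptoms for QUIP-RS.

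**The concern.** An instrument that supports a diagnosis in the individual is there to find individuals. The harm of interest is a new or worse problem in some subjects, and summaries of a continuous score do not say how many there are. Rises in a few subjects can be offset by small falls in others, leaving the mean and median near zero. A subject who worsens and leaves contributes nothing to later visits.

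At stake is how well a stated safety objective is answered. The extension-visit assessment lists (Protocol 9.2.6 and 9.2.7) do not include QUIP-RS, so the 12-month data are its only scheduled on-treatment series. An analysis added after the SAP is final would go to the study report's appendices as exploratory (SAP 3.5.2).

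**Working it through.** The documents give no QUIP-RS rate, SD, cut-off or power figure, so there is no planned number to reproduce. The check has three parts.

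**1. How the SAP treats its other measures**

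- ESS (7.5): proportions scoring 10 or more and 18 or more.
- C-SSRS (7.5): frequency and percentage for each response.
- VAS pain (7.3.2): proportions above 0 mm and at 40 mm or more.
- Laboratory values (7.5.1): normal/abnormal counts and potentially clinically significant limits.
- Orthostatic hypotension (7.5.2): proportion and shift table.
- QTc (7.5.3): counts against five criteria.
- EQ-5D-5L dimensions (8.2.7): improved, same or worsened at each visit.
- QUIP-RS (7.5): continuous summaries only.

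**2. What the planned statistics would show**

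Numbers of subjects come from the documents: 120-170 (SAP 3.3) and about 210 (Protocol 11.2). All changes in score are assumed.

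*Example A, N = 150 (within the SAP range).* Six subjects rise by 12, 40 fall by 2, 104 are unchanged.

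- Mean change = (6 × 12 − 40 × 2)/150 = −8/150 = −0.053. Median = 0, since 104 of 150 are 0.
- SD = √[(6 × 144 + 40 × 4 − 150 × 0.0533²)/149] = 2.62. Maximum = +12.
- If the six had not changed: mean = −80/150 = −0.53, SD = √[(160 − 150 × 0.5333²)/149] = 0.89, maximum = 0.
- A count would show 6/150 = 4.0%.

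*Example B, N = 210.* Five subjects rise by 10, 50 fall by 1, 155 are unchanged.

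- Mean = (50 − 50)/210 = 0.00, median = 0, SD = √(550/209) = 1.62, minimum −1, maximum +10.
- A count would show 5/210 = 2.4% (exact 95% CI 0.8% to 5.5%). Five cases in 170 would be 2.9% (1.0% to 6.7%), and in 120, 4.2% (1.4% to 9.5%).

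*Range.* For k cases each rising by r, the fall per remaining subject that brings the mean to zero is k × r/(N − k). Over N = 120 to 210, k = 3 to 10 and r = 8 to 20, this runs from 3 × 8/207 = 0.12 to 10 × 20/110 = 1.82 points. With five cases in 210 it is 5 × 8/205 = 0.20 to 5 × 20/205 = 0.49. With no offset, those five cases move the mean by only 5 × 8/210 = 0.19 to 5 × 20/210 = 0.48.

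So the mean and median can stay near zero. The SD and maximum do react. But the maximum is one subject's value, +12 in Example A whether one subject or six rose that far, and the SD mixes rises and falls. Neither gives a number of subjects.

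**3. Subjects who leave**

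QUIP-RS is collected at early termination. SAP 5.4 moves early-termination data into the closest missing visit, but that rule is listed under the efficacy endpoint. Safety data are summarised as observed (5.4) and as collected at scheduled visits (5.5). No stated rule says whether, or where, an early-termination QUIP-RS score enters a by-visit safety table.

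**The case against.** The strongest reply is that cases are not lost.

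- **The plan is not limited to means.** A reader might infer that only group means and mean changes are reported. SAP 5.1 does not support that: median, SD, minimum and maximum are planned, and SAP 7.5 applies descriptive statistics to every domain as well as the totals the protocol names. In Example A the SD roughly triples, from 0.89 to 2.62, and the maximum goes from 0 to +12.
- **Subject-level information exists elsewhere.** All data are listed. Impulse-control events reported as adverse events get subject counts, percentages and exposure-adjusted rates (SAP 7.3.4). Discontinuation due to a TEAE is a tolerability measure (SAP 7.4.1), and sites must rule out an adverse event when a subject withdraws consent or leaves for another reason (Protocol 8.3.4).
- **The comparators have limits to use.** ESS has a stated cut-off and C-SSRS is categorical by construction. The documents give no cut-off for QUIP-RS.
- **A worst-visit count has its own bias.** With eight scheduled post-baseline visits to Month 12, a single lowest-grade answer at one of them would count as new.

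Most of this stands, and it limits the point. It does not close the gap. Listings give no count and no definition of a case. Adverse events are elicited by a non-leading question (Protocol 10.1.1), nothing turns a QUIP-RS rise into an adverse event, and impulse-control events are not of special interest (Protocol 10.1.1.1, SAP 7.3.1). The missing cut-off is not a barrier either, since the SAP's own formats for VAS pain (above 0) and EQ-5D-5L (improved/same/worsened) need none. The noise argument is sound and belongs beside the added table.

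**Conclusion.** The point holds in a limited form. SAP 7.5 plans no subject-level count or shift for QUIP-RS, so the tables may not show how many subjects developed impulsive-compulsive symptoms. The SD, maximum, listings and reported TEAEs show this only partly, and the handling of early-termination scores is unstated.

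A reader might go further and conclude that the report would give false reassurance. The documents do not support that, given the other routes to the same cases. Nor do they support a premise that most subjects score near 0: Protocol 10.1.10 gives only the 0 to 4 response anchors. Offsetting changes do not need that premise.

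The sizes above (2.4% to 4.2% of subjects with a mean change of about 0) rest on assumed rises and falls. They show what is possible and predict nothing. No alpha, power or sample-size figure is affected. This is a secondary measure in an open-label descriptive study, and the change is desirable rather than essential.

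**What to change.** Add one table to SAP 7.5, by regimen and cohort, for the ICD total (A-D), each of A to F and the overall total. The denominator is Safety Set subjects with a baseline and at least one post-baseline QUIP-RS. Report:

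- (a) the number and percentage with a score of 0 at baseline and above 0 at any scheduled or early-termination assessment up to Month 12;
- (b) improved, same and worsened counts by visit, and the quartiles and maximum of each subject's worst post-baseline change.

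Include unscheduled assessments only as a stated exception to SAP 5.1, which keeps them out of summary tables. Say whether the first safety follow-up visit of an early leaver counts. Note that for Cohort 1 the baseline under SAP 5.2 precedes dosing in ND0612H-006, which is a further reason to show the cohorts separately.

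The cost is one table, with no change in conduct or data collection. QUIP-RS is not taken at every clinic visit (Day 2 and the extension visits do not list it), but the scheduled visits and early termination are enough. SAP 1 allows an update before final database lock.

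State the downside with the table: a worst-of-several-visits count picks up mild rating noise in the upward direction and has no untreated control. It should be read with the change distribution, and as descriptive only.
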